13.7.1 Primary Endpoint Stratified by Components of the Composite Endpoint

Differences in success rates between HM3 and HM II will be performed for each component of the composite endpoint to evaluate if a single component is influencing the outcome. Specifically, for each component, two-sided 95% confidence intervals of the differences and a z-test of proportions will be generated using the normal approximation to the binomial distribution.

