13.4 Randomization

Subjects will be randomized in a 1:1 fashion (1 HM3: 1 HM II). The randomization will be stratified by study center and blocked to maintain the 1:1 ratio over time. Randomization will be implemented through the Electronic Data Capture (EDC) system. Study centers will be allowed a maximum of 50 randomized Subjects. Centers may have their maximum enrollment number increased with prior Sponsor approval. An analysis will be conducted to determine if there is site bias. Subjects will be considered enrolled in the study upon signing informed consent; all subjects will be randomized and will be included in the intent-to-treat analysis.

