13.5.2 Short Term Indication

Based on a review of recent INTERMACS and Thoratec data, it is assumed that the HM II will achieve a composite success rate of 85% at 6 months. It is also assumed that the HM3 will have a composite success rate of 87% due to less pump replacements at 6 months caused by thrombus or driveline issues. It will take 276 total Subjects to achieve 80% power to prove the HM3 is non-inferior to HM II when the margin of non-inferiority is -10% ($=\Delta$ in the above null and alternative hypotheses) using the Farrington-Manning risk difference approach to non-inferiority at a one-sided alpha = 0.025.

INTERMACS HM II data from 26 sites likely to participate in the HM3 IDE study was reviewed. Eight hundred and twenty (820) patients were implanted with the HM II in 2012 at these sites and 52 (6%) received a transplant or explant due to myocardial recovery prior to 6 months. In order to have sufficient data to evaluate the 6 month success rate, an additional 9 Subjects will be randomized per arm (6% of 138) to account for these early outcomes. This results in 294 total Subjects.

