8.4.2 Short Term Indication

Based on a review of recent INTERMACS and Thoratec data, it is assumed that the HM II will achieve a composite success rate of 85% at 6 months. It is also assumed that the HM III will have a composite success rate of 87% due to less pump replacements at 6 months caused by thrombus or driveline issues. It will take 138 HM III and 138 HM II Subjects (276 total Subjects) to achieve 80% power to prove the HM III is non-inferior to HM II when the margin of non-inferiority is -10% ($=\Delta$ in the above null and alternative hypotheses) using the Farrington-Manning risk difference approach to non-inferiority at a one-sided alpha = 0.025.

INTERMACS HM II data from 26 sites likely to participate in the HM III IDE study was reviewed. Eight hundred and twenty (820) patients were implanted with the HM II in 2012 at these sites and 52 (6%) received a transplant or explant due to myocardial recovery prior to 6 months. In order to have sufficient data to evaluate the 6 month success rate, an additional 9 Subjects will be randomized per arm (6% of 138) to account for these early outcomes. This results in a total of 147 Subjects randomized in each arm (294 total Subjects).

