8.6 Analysis of Primary Endpoint

The HM III will be considered non-inferior to the HM II for both short and long term indications if the lower two-sided 95% confidence limit of the risk difference in the composite success between treatment arms (HM III minus HM II) is greater than -10% ("negative 10%", where 10% is the non-inferiority Δ in the above null and alternative hypotheses). Once non-inferiority is inferred, the data will be analyzed for superiority at a one-sided 0.025 level of significance using closed testing methods via the z-test of proportions using the normal approximation to the binomial distribution. Since the short term and long term evaluations are two distinct endpoints, no adjustment for multiple comparisons is required. The long-term evaluation will only be made if the HM 3 is non-inferior to the HM II for the short-term indication, thus no adjustment to alpha will be made.

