8.6.1 Primary Endpoint Stratified by Components of the Composite Endpoint

Differences in success rates between HM III and HM II will be performed for each component of the composite endpoint to evaluate if a single component is influencing the outcome. Specifically, for each component, two-sided 95%

confidence intervals of the differences and a z-test of proportions will be generated using the normal approximation to the binomial distribution.

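### Normal-approximation intervals and z-tests are fixed for every component of the composite with no provision for sparse counts, so at 6 months the intervals for rare components may be too narrow

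*Protocol*

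**What the plan says.** Protocol 13.7.1 compares the arms on each component of the composite "to evaluate if a single component is influencing the outcome". The method is fixed for all components alike: "two-sided 95% confidence intervals of the differences and a z-test of proportions will be generated using the normal approximation". SAP 8.6.1 has the same rule: "confidence intervals of the differences and a z-test of proportions will be generated using the normal approximation to the binomial distribution". Neither section has an exact, score or zero-count alternative, and neither lists the rows of the table.

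The failure definitions (Protocol 13.3.1, SAP 8.2.1) include death, stroke with a modified Rankin Score above 3, device replacement, exchange or deactivation, urgent transplant for LVAS malfunction, and withdrawal. SAP 8.4.2 sets the short-term cohort at 147 per arm. Protocol 13.5.2 attributes the expected benefit to one component: "HM3 will have a composite success rate of 87% due to less pump replacements at 6 months caused by thrombus or driveline issues".

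Elsewhere the plan does use an exact test: Fisher's for 24-month pump replacement (Protocol 13.17, SAP 8.16) and, as appropriate, for adverse events (Protocol 13.10, SAP 8.9).

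**The concern.** The usual normal-approximation interval for a difference in proportions (Wald) takes its variance from the observed proportions. With very few events that variance is too small, and with none in either arm it is zero. Pump replacement is the component through which HM3 is expected to do better, so a reader will look first at that row. If its interval is too short, or its z-test signals a difference on a handful of events, the table answers its own question poorly. Pump replacement would also be tested by a cruder method at 6 months, where counts are small, than at 24 months in 1028 Subjects, where they are larger.

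**Working it through.** **Cohort size.** The Farrington-Manning formula with 87% v 85%, a margin of 10%, one-sided alpha 0.025 and 80% power has restricted estimates of 0.794 and 0.894. It gives 137.86, so 138 per arm (276 in total, as stated). Adding 9 per arm gives 147.

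**Expected counts at 6 months (not given in the documents).**
- Assumption: constant hazard from the 24-month rates of 3% and 7%. HM3: 1 - 0.97^(1/4) = 0.76%, and 147 x 0.0076 = 1.1 events. HM II: 1 - 0.93^(1/4) = 1.80%, and 147 x 0.0180 = 2.6 events.
- If the whole 2-point gain (85% to 87%) comes from replacements, the HM II rate is at least 2%, or 147 x 0.02 = 2.9 events.
- Protocol section 23 cites 94% freedom at 6 months from pump exchange or thrombosis death. Read as counting all exchanges, that caps HM II at 147 x 0.06 = 8.8.
- Death has a ceiling of 11% in Table 1, about 16 per arm, and is not sparse. No rate is given for urgent transplant for malfunction, which may be rarer than replacement, or for stroke with a Rankin score above 3.

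**Intervals for HM3 minus HM II, percentage points, 147 per arm.** Wald is p1 - p2 ± 1.96 x sqrt[p1(1-p1)/147 + p2(1-p2)/147].

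| Events | Wald | Miettinen-Nurminen | Newcombe |
|---|---|---|---|
| 0 v 0 | 0.00 to 0.00 | -2.56 to 2.56 | -2.55 to 2.55 |
| 0 v 1 | -2.01 to 0.65 | -3.76 to 1.88 | -3.75 to 1.93 |
| 0 v 3 | -4.33 to 0.24 | -5.84 to 0.54 | -5.83 to 0.84 |
| 0 v 4 | -5.35 to -0.09 | -6.80 to -0.13 | -6.79 to 0.32 |
| 3 v 3 | -3.23 to 3.23 | -4.04 to 4.04 | -4.02 to 4.02 |

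**Coverage by full binomial enumeration, 147 per arm.**

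| True rates, HM3 v HM II | Wald | Larger one-sided Wald miss (nominal 2.5%) | Miettinen-Nurminen | Newcombe |
|---|---|---|---|---|
| 0.76% v 1.80% | 91.9% | 7.4% | 97.3% | 98.6% |
| 1% v 3% | 93.1% | 5.9% | 93.9% | 97.0% |
| 2% v 4% | 94.4% | 4.1% | 94.3% | 96.3% |
| 1% v 1% | 97.2% | 1.4% | 97.2% | 99.2% |
| 2% v 2% | 95.4% | 2.3% | 95.4% | 97.2% |

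In the unequal rows the larger Wald miss is at the lower limit: the interval lies wholly above the true difference, so it understates HM3's advantage.

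**Zero width.** This needs no event in both arms. At 0.76% v 1.80% the probability is 0.9924^147 x 0.9820^147, about 2.3%. If HM II is at least 2%, it is at most 0.98^147 = 5.1%. The pooled z-test is then 0/0.

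**Test at 0 v 4.** The pooled proportion is 4/294 = 0.0136. z = (4/147) / sqrt(0.0136 x 0.9864 x 2/147) = 2.01, so p = 0.044. Fisher's exact test gives p = 0.12.

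**The case against.** The case against is strong on size. No document gives a 6-month component rate, and the even spread fits the plan's own 6-month figures poorly: it gives a gap of 1.80 - 0.76 = 1.04 points, where Protocol 13.5.2 attributes 2 points to replacements, and it puts HM II well below the 6% implied in section 23. With a 2-point gap and somewhat higher rates the defect largely disappears: at 2% v 4%, Wald and Miettinen-Nurminen both cover about 94.4%. At 24 months, with 3% v 7% and 183 per arm, they cover 94.8% and 95.0%. The score interval is not perfect either; at 1% v 3% its larger one-sided miss is 4.0%. Neither document says Wald, and a score interval also rests on a normal approximation. The confirmatory comparison of pump replacement already uses Fisher's test. All of this stands and limits the point.

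It does not remove it. A method is prescribed for every component, its usual reading performs poorly at counts the plan makes plausible, and the ambiguity of the term is itself a reason to name the interval.

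A reader might also infer three stronger points, none of which is supported:
- That components will have 0 to 3 events per arm. This is plausible for HM3 replacement and urgent transplant, uncertain for HM II replacement (2.6 to 8.8) and debilitating stroke, and wrong for death.
- That one empty arm makes the interval collapse. With 0 v 1 the Wald width is still 2.66 points.
- That the one-sided error is generally about three times nominal. That holds only near 0.76% v 1.80%.

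**Conclusion.** The point holds as a modest defect in a supportive analysis. At 0 to 3 events per arm the non-zero Wald intervals computed are about 20% to 53% shorter than Miettinen-Nurminen intervals. Coverage falls to 91.9% at 0.76% v 1.80% and 93.1% at 1% v 3%, with little or no loss from about 2% v 4% upward and none at equal rates of 1-2%. The z-test can fall below 0.05 on counts where Fisher's test does not, although part of that gap reflects the conservatism of Fisher's test.

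These figures rest on reading the normal approximation as Wald, on 147 per arm, and on assumed 6-month rates. The cap of 8.8 HM II events assumes that the cited 94% counts every exchange.

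It would be wrong to infer that the primary decision is compromised. Protocol 13.7 and SAP 8.6 do not name the method for the limit ("if the lower two-sided 95% confidence limit of the risk difference in the composite success between treatment arms"), but sizing and the interim statistic use Farrington-Manning. Even a Wald limit would have a one-sided error of 0.0263 to 0.0275 (control success 85-90%) against 0.0247 to 0.0252 for Farrington-Manning, at most about 0.25 percentage points above nominal.

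**What to change.** In Protocol 13.7.1 and SAP 8.6.1, replace the normal-approximation interval with one named score-type interval (Miettinen-Nurminen or Newcombe) for every component difference. Use Fisher's exact test for components with small expected counts, below a stated cut-off such as 5, as the plan already does for 24-month pump replacement. The choice of interval should be fixed in advance, because the two can differ: at 0 v 4 Miettinen-Nurminen excludes zero while Newcombe includes it and agrees with Fisher's test. Newcombe is the more conservative, with coverage of at least 96% in every sparse scenario tried.

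Optionally, name the Farrington-Manning limit in Protocol 13.7 and SAP 8.6, so that sizing, interim and final decision share one statistic.

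The cost is wording and standard software options, with no extra patients or data. The downside is slightly wider intervals and a more conservative test for sparse components. The non-inferiority decision, alpha and sample size stay as they are.

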13.7.2 Effect of Site Bias on the Primary Endpoint

In order to determine if a few superior investigational sites are influencing the primary endpoint results, a comparison of results across sites will be performed. Specifically, for each of the short term and long term outcomes, the significance of the treatment-by-site interaction effect will be assessed using logistic regression with the main effects for treatment and site, and with a treatment-by-site interaction effect. The treatment-by-site interaction effect will be tested at the 0.15 level of significance. A non-significant interaction or an interaction that is significant but only quantitative and not qualitative in nature will support the pooling of Subjects across sites for the primary analyses. Given that a number of sites will contribute only small numbers of Subjects, we will pool sites with less than 5 Subjects for the analysis.

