7 NUMBER OF CLINICAL SITES AND SUBJECTS

The study will be conducted in up to 70 clinical sites. The total sample size for this study is 1028 Subjects. Three hundred and sixty-six (366) Subjects will be enrolled and randomized to evaluate the primary endpoint. The data from the Subjects randomized for the primary endpoint will be used for PMA submission for the Short Term and Long Term indications. An additional 662 Subjects will be randomized to achieve 1028 Subjects needed for the powered secondary endpoint analysis. The data from the powered secondary endpoint will be used to update labeling under a Supplemental PMA. Refer to Figure 2.

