where $Z_{0.20}$ is the 20th percentile of the standard normal distribution (= -0.84) and where all other variables in this equation are defined above. This formula assumes the interim observed effect size between treatments is the true effect size between treatments.

Note that the final sample size for the 6-month short-term outcome will NOT be decreased below the currently planned final sample size for the 6-month short-term outcome. According to Chen, Demets and Lan (2004), in order to maintain Type I error at the nominal level, the sample size will not be increased to beyond a percentage of the original sample size as determined by the bound R , where R satisfies:

$$\frac{\sqrt{1+R}(\sqrt{1+R}-1)}{\sqrt{(1+R)-t}} = \left(\frac{|Z_{0.20}|}{Z_{1-\alpha}} \right).$$

With $|Z_{0.20}| = 0.84$ and $Z_{1-\alpha} = 1.96$, it can be shown that $R = 1.513$, which means the sample size can increase up to 151.3% of the original planned sample size (up to 369 per group) without inflating Type I error.

Also, any sample size increase for the 6-month short term outcome will also be applied to the final sample size used to assess the long-term outcome (there will be no interim unblinded analysis on the long-term outcome). The following table displays the sample size scenarios for each of the long-term and short-term outcome under various situations:

Endpoint	Sample Size Per Group at Interim	Sample Size Per Group at Final Analysis	
		In the Event of No Sample Size Increase at Interim	In the Event of a Sample Size Increase of X at Interim
6-month Short Term	After 74 patients per group are treated and followed for 6 months	After 147 patients per group are treated and followed for 6 months	After 147 + X patients per group are treated and followed for 6 months
24-month Long Term	This endpoint will not be analyzed in the interim.	After 183 patients per group are treated and followed for 24 months.	After 183 + X patients per group are treated and followed for 24 months.

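### The treatment-by-site test at 0.15 does not hold its level with sites this small, its statistic is not named, and the unfavourable branch is missing

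*Protocol*

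**What the plan says.** Protocol 13.7.2 gives the purpose: "In order to determine if a few superior investigational sites are influencing the primary endpoint results". For each of the 6- and 24-month outcomes it fits a logistic regression with treatment, site and their interaction. "The treatment-by-site interaction effect will be tested at the 0.15 level of significance." It then says that "A non-significant interaction or an interaction that is significant but only quantitative and not qualitative in nature will support the pooling of Subjects across sites". On small sites, "we will pool sites with less than 5 Subjects for the analysis". SAP 8.6.2 repeats this and adds nothing.

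Neither document names the statistic (likelihood-ratio, Wald, score or exact) or its degrees of freedom when a site has no successes or no failures. Neither defines qualitative, or says what is done after a significant qualitative interaction.

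The number of sites in the analysis is not fixed. Protocol 13.5.2 says "INTERMACS HM II data from 26 sites likely to participate in the HM3 IDE study was reviewed". Protocol 7 says "The study will be conducted in up to 70 clinical sites", a ceiling for all 1028 Subjects. Protocol 13.4 caps a centre at 50, but "Centers may have their maximum enrollment number increased with prior Sponsor approval".

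**The concern.** A pool-below-5 rule leaves many site units with only a few Subjects per arm. The chi-square approximation with one degree of freedom per extra site is then poor, and the usual statistics fail in opposite directions. With small counts the likelihood-ratio statistic runs above its reference distribution. The Wald statistic gives little or no weight to the most extreme sites, because their estimated variances are very large. The same data could therefore be reported as showing interaction or as supporting pooling, depending on an unnamed choice.

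At stake is the plan's own assurance that pooling is justified and that no few sites carry the result. SAP 8.7 does not replace it: it looks at site only among Subjects surviving to 730 days, and at a learning curve within HM3.

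**Working it through.** **Inputs from the documents.** Long term: 366 Subjects, 50% HM II and 55% HM3. Short term: 294 Subjects, 85% and 87%. Allocation is 1:1, blocked within centre; cap 50; sites under 5 pooled; level 0.15.

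**Assumed.** 15, 26, 40, 50, 60 or 70 sites; equal, moderately unequal (gamma shape 2) or strongly unequal (gamma shape 1) sizes; blocks of 4; sites under 5 form one unit; site-intercept SD on the logit scale 0, 0.5 or 1.0, with overall success rates held at the plan's values. This gives 6 x 3 x 3 = 54 settings per time point.

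**The plan's own figure.** The 0.15 has no derivation, but the long-term sample size reproduces: (1.960 + 0.842)² x (0.50 x 0.50 + 0.55 x 0.45) / (0.05 + 0.10)² = 7.849 x 0.4975 / 0.0225 = 173.5, so 174 per arm and 348 in total. Adding 9 per arm gives 366.

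**How sparse the cells are.**
- 24 months, 26 sites: 366 / 26 = 14.1 per site, about 7 per arm. The chance that an arm of 7 has all successes or all failures is 2 x 0.5⁷ = 1.6% (HM II) and 0.55⁷ + 0.45⁷ = 1.9% (HM3). So about 26 x 0.034 = 0.9 sites have a zero cell even when all sites are equal in size.
- 6 months, 26 sites: 294 / 26 = 11.3 per site, about 5.65 per arm. Expected failures per arm are 5.65 x 0.13 = 0.73 and 5.65 x 0.15 = 0.85. In simulation, on average 4.75 + 12.8 = 17.5 of 26 sites had no information or a zero cell.

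**Statistics**, for K units with K - 1 degrees of freedom:
- Likelihood-ratio: deviance of the treatment-plus-site model against the saturated model.
- Wald: sum of w(L - weighted mean of L)², where L is the site log odds ratio and 1/w is the sum of the four reciprocal cell counts; units with a zero cell get weight zero.
- Score: Pearson chi-square of the treatment-plus-site model.
- Zelen: conditional on each site's margins and on total HM3 successes, the tables have probability proportional to the product over sites of C(n₁, a) x C(n₀, m - a). The p-value is the total probability of tables no more likely than the one observed. It does not depend on the common odds ratio.

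**Rejection rates with no true interaction, nominal 15%** (2000 trials per setting, SE at most 1.1 points; Zelen 1000 trials, SE 1.1):

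| Setting | Likelihood-ratio | Wald | Score |
|---|---|---|---|
| 24 months, 15 sites | 21-27% | 1-12% | 16-19% |
| 24 months, 26 sites | 31-37% | 0-2% | within next row |
| 24 months, 26-70 sites, by SD 0 / 0.5 / 1.0 | 40-70 unequal sites: 42-63 / 41-59 / 36-50% | 0-2% | 21-46 / 20-37 / 15-19% |
| 24 months, 70 equal sites, by SD 0 / 0.5 / 1.0 | 94 / 91 / 75% | within row above | within row above |
| 6 months, all | 0-35% | 0% | 0-11% |

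Zelen gave 13-17% at 24 months and 13-18% at 6 months over the 54 settings each.

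In all 54 settings at 24 months the likelihood-ratio test was above 15% and Wald below it. A separately programmed run at 26 sites gave 32-39% and 0.3-2.0%; direct individual-level fits gave 33.3% and 2.1%. The degrees of freedom matter too. If only informative sites are counted, the 6-month score test rises to 17-19% at 26 sites and 21-48% at 60.

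**Power.** With a true between-site log-odds-ratio SD of 1.0 at 24 months, Wald rejects in 10-23% of trials with 26 unequal sites and 0-1% with 50-70. Zelen rejects in 62-81% over 26-70.

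**Sign reversal.** With no interaction, at least one site unit has the opposite sign in 97-100% of trials, so observed reversal cannot define qualitative.

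**Leave-one-site-out, 24 months.** With no interaction, dropping the most influential site lowers the limit by a median of 1.4-3.3 points, and 9-27% of passing trials have at least one limit at or below -10%. With one assumed driving site (largest site HM3 85%, HM II 25%; all others 45% and 50%) the figures are 6.5-9.1 points and 72-81%.

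**After re-estimation.** SAP 8.6.3 says "the sample size can increase up to 151.3% of the original planned sample size (up to 369 per group) without inflating Type I error". That is 147 x 2.513 = 369, an increase of 222, so 183 + 222 = 405 per group long term. The 24-month likelihood-ratio rate is then 25-56% and Wald 0-6%; Zelen is 12-19% (300 trials, SE 2.1).

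**The case against.** The primary decision in Protocol 13.7 and SAP 8.6 is not conditional on this test, so no estimate, limit or sample size changes. That stands, and it sets how much the point weighs.

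A significant result does not by itself defeat pooling; it must also be qualitative. How often a null trial would lose support for pooling is therefore unknown. That is correct, but it follows from the missing definition. It is also implied that a significant qualitative interaction does not support pooling; what is absent is the action and the criterion.

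With few, large sites the problem shrinks. At 8 sites and 24 months the likelihood-ratio test rejects in 16-18% and Wald in 14-15%; at 12 sites, 19-22% and 8-14%. But Protocol 13.7.2 itself expects a number of small sites, and at 6 months Wald is about 0% even with 8.

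The likelihood-ratio test would catch a driving site: in the assumed example, with 26 and 50 unequal sites, it rejects in 90-97% of trials, Zelen in 63-94% and Wald in 0-58%. So naming a statistic and avoiding Wald would remove the worst harm. Part of the likelihood-ratio advantage is its inflated level, however, and it would still not be a test at 0.15.

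Two smaller points stand. The remedy gives no formal criterion for qualitative. It also does not say how an exact p-value is combined across multiple imputations, although counting withdrawals as failures limits what has to be imputed.

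**Conclusion.** The concern holds. With the stated pooling rule, neither the likelihood-ratio nor the Wald test has the stated 0.15 level at 24 months in any layout of 15 to 70 sites that was simulated. At 26 sites the rates are 31-37% and 0-2%. The score test is near nominal only when baseline success differs strongly between sites or sites are few. The missing statistic, the missing branch and the undefined term can be read from the text without simulation.

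The figures rest on assumed site numbers, sizes, block size and between-site variation; they are what these settings gave, not bounds. About 8 sites near the cap would remove most of the 24-month problem. This is a fault in a supporting check that should be corrected, not a threat to the primary conclusion.

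**What to change.** Change Protocol 13.7.2 and SAP 8.6.2 as follows.

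1. Keep 0.15 and the site units, but replace the large-sample test with an exact or Monte Carlo conditional (Zelen) test of equal odds ratios across sites. Add a line on how imputed outcomes enter it.
2. Whatever the test shows, report the lower 95% confidence limit of the risk difference leaving out each site in turn. Label it descriptive; the decision rule is unchanged.
3. Do not judge qualitative by observed sign reversals. State the missing branch: if the test is significant, say so and discuss pooling alongside the leave-one-site-out limits.

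The cost is wording and a different test call, with no new data. Power is limited, mostly at 6 months: with a between-site log-odds-ratio SD of 0.5 / 1.0 and 26-70 unequal sites, Zelen rejects in 26-37% / 62-81% of trials at 24 months and 18-24% / 33-49% at 6 months. Leave-one-site-out limits cross -10% by chance in 9-27% of passing trials, so they must not become a pass/fail rule.

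A simpler option is to pool sites under 20. With 26 unequal sites at 24 months this brings the likelihood-ratio test to 19-20%, score to 15-18% and Wald to 7-15%. But it puts 39-50% of Subjects in one unit (61-96% with 40-70 unequal sites), and at 6 months leaves likelihood-ratio at 17-25% and Wald at 1-2%. With 50 unequal sites and SD 1.0 its likelihood-ratio power is 42-58%, against 69-73% for Zelen.
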